# **10 Source Documents and Access to Source Data/Documents**

Source data is all information, original records of clinical findings, observations, or other activities in a clinical trial necessary for the reconstruction and evaluation of the trial. Source data are contained in source documents. Examples of these original documents, and data records include: hospital records, clinical and office charts, laboratory notes, memoranda, subjects' diaries or evaluation checklists, pharmacy dispensing records, recorded data from automated instruments, copies or transcriptions certified after verification as being accurate and complete, microfiches, photographic negatives, microfilm or magnetic media, x-rays, subject files, and records kept at the pharmacy, at the laboratories, and at medico-technical departments involved in the clinical trial.

The study CRF is the primary data collection instrument for the study. All data requested on the CRF must be recorded. All missing data must be explained. If a space on the CRF is left blank because the procedure was not done or the question was not asked, write "N/D". If the item is not applicable to the individual case, write "N/A". All entries should be printed legibly in black ink. If any entry error has been made, to correct such an error, draw a single straight line through the incorrect entry and enter the correct data above it. All such changes must be initialed and dated. DO NOT ERASE OR WHITE OUT ERRORS. For clarification of illegible or uncertain entries, print the clarification above the item, then initial and date it.

Access to study records will be limited to IRB-approved members of the study team. The investigator will permit study-related monitoring, audits, and inspections by the IRB/EC, the sponsor, government regulatory bodies, and University compliance and quality assurance groups of all study related documents (e.g. source documents, regulatory documents, data collection instruments, study data etc.). The investigator will ensure the capability for inspections of applicable study-related facilities (e.g. pharmacy, diagnostic laboratory, etc.).

Participation as an investigator in this study implies acceptance of potential inspection by government regulatory authorities and applicable University compliance and quality assurance offices.

# **11 Ethics/Protection of Human Subjects**

# 11.1 Ethical Standard

The investigator will ensure that this study is conducted in full conformity with Regulations for the Protection of Human Subjects of Research codified in 45 CFR Part 46.

# 11.2 Institutional Review Board

The protocol, informed consent form(s), recruitment materials, and all participant materials will be submitted to the IRB for review and approval. Approval of both the protocol and the consent form must be obtained before any participant is enrolled. Any amendment to the protocol will require review and approval by the IRB before the changes are implemented to the study. All changes to the consent form will be IRB approved; a determination will be made regarding whether previously consented participants need to be re-consented.

# 11.3 Informed Consent Process

# 11.3.1 Consent/Assent and Other Informational Documents Provided to Participants

Consent forms describing in detail the study intervention, study procedures, and risks are given to the participant and written documentation of informed consent is required prior to starting intervention.

# **11.3.2 Consent Procedures and Documentation**

Informed consent is a process that is initiated prior to the individual's agreeing to participate in the study and continues throughout the individual's study participation. Extensive discussion of risks and possible benefits of participation will be provided to the participants and their families. Consent forms will be IRBapproved and the participant will be asked to read and review the document. The investigator will explain the research study to the participant and answer any questions that may arise. All participants will receive a verbal explanation in terms suited to their comprehension of the purposes, procedures, and potential risks of the study and of their rights as research participants. Participants will have the opportunity to carefully review the written consent form and ask questions prior to signing. The participants should have the opportunity to discuss the study with their surrogates or think about it prior to agreeing to participate. The participant will sign the informed consent document prior to any procedures being done specifically for the study. The participants may withdraw consent at any time throughout the course of the trial. A copy of the signed informed consent document will be given to the participants for their records. The rights and welfare of the participants will be protected by emphasizing to them that the quality of their medical care will not be adversely affected if they decline to participate in this study.

A copy of the signed informed consent document will be stored in the subject's research record. The consent process, including the name of the individual obtaining consent, will be thoroughly documented in the subject's research record. Any alteration to the standard consent process (e.g. use of a translator, consent from a legally authorized representative, consent document presented orally, etc.) and the justification for such alteration will likewise be documented.

# 11.4 Participant and Data Confidentiality

Information about study subjects will be kept confidential and managed according to the requirements of the Health Insurance Portability and Accountability Act of 1996 (HIPAA). Those regulations require a signed subject authorization informing the subject of the following:

- What protected health information (PHI) will be collected from subjects in this study
- Who will have access to that information and why
- Who will use or disclose that information
- The rights of a research subject to revoke their authorization for use of their PHI.

In the event that a subject revokes authorization to collect or use PHI, the investigator, by regulation, retains the ability to use all information collected prior to the revocation of subject authorization. For subjects that have revoked authorization to collect or use PHI, attempts should be made to obtain permission to collect at least vital status (i.e. that the subject is alive) at the end of their scheduled study period.

All the MRI data will be archived into the research image database in the Department of Radiology at the New York University Medical Center. [name] (PI) will monitor all the MRI data and save the data on the NYU Radiology password-protected server. A copy of the data will be kept on the P.I.'s workstation, which has a secure password protection. Every attempt will be made by [name] to maintain all information collected in this study strictly confidential, except as may be required by court order or by law. All clinical and exercise-related data will be de-identified and stored at the Arthur J. Nelson Jr. Human Performance Lab at the Department of Physical Therapy. All digital materials will be stored on a secure password protected server with access given only to authorized study personnel. All paper documents will be stored for three years in a locked file cabinet and lab, with access given only to authorized study personnel. [name] will work with the Data Services and Data Management Planning Team

#### CONFIDENTIAL

(http://guides.nyu.edu/data\_management) to develop and implement this plan. Authorized representatives of the New York University Institutional Review Board (IRB), a committee charged with protecting the rights and welfare of research subjects, may be provided access to medical or research records that identify subjects by name. In any publication or presentation resulting from this research, the subjects will not be identified by name. Any serious adverse effects to the participants will be immediately communicated to the IRB as well as our departmental research committee that oversees clinical research

# 11.5 Data Collection and Management Responsibilities

Data collection is the responsibility of the clinical trial staff at the site under the supervision of the site PI. The investigator is responsible for ensuring the accuracy, completeness, legibility, and timeliness of the data reported.

All source documents should be completed in a neat, legible manner to ensure accurate interpretation of data. Black ink is required to ensure clarity of reproduced copies. When making changes or corrections, cross out the original entry with a single line, and initial and date the change. DO NOT ERASE, OVERWRITE, OR USE CORRECTION FLUID OR TAPE ON THE ORIGINAL.

# 11.6 Study Records Retention

Study documents will be retained for the longer of 3 years after close out or 5 years after final reporting/publication. These documents should be retained for a longer period, however, if required by local regulations. No records will be destroyed without the written consent of the NIH, if applicable. It is the responsibility of the NIH to inform the investigator when these documents no longer need to be retained.

# 11.7 Protocol Deviations

A protocol deviation is any noncompliance with the clinical trial protocol or GCP requirements. The noncompliance may be either on the part of the participant, the investigator, or the study site staff. As a result of deviations, corrective actions are to be developed by the site and implemented promptly.

It is the responsibility of the site to use continuous vigilance to identify and report deviations within 5 working days of identification of the protocol deviation. Protocol deviations must be reported to the local IRB per their guidelines. The site PI/study staff is responsible for knowing and adhering to their IRB requirements.

# **12 Study Finances**

## 12.1 Funding Source

This study is financed through a grant R01DK114428 from the National Institute of Diabetes and Kidney Disease (NIDDK)

# 12.2 Costs to the Participant

There will be no cost to the participant for enrolling in this study.

## 12.3 Participant Reimbursements or Payments

Each participant will be offered \$500 upon completion of the 10-week supervised exercise intervention. They will also receive a clincard (similar to a debit/credit card) of \$50 for undergoing each MRI scan (two in total) and up to \$20 reimbursement for travel to our facilities.

If attendance during the exercise phase drops below 80%, reimbursement will be prorated based on the number of sessions completed. Participants will receive \$17 per session.

# **13 Conflict of Interest Policy**

Any investigator who has a conflict of interest with this study (patent ownership, royalties, or financial gain greater than the minimum allowable by their institution, etc.) must have the conflict reviewed by the NYU Langone Conflict of Interest Committee with a Committee-sanctioned conflict management plan that has been reviewed and approved by the study sponsor prior to participation in this study. All NYULMC investigators will follow the applicable conflict of interest policies.

# Attachments

These documents are relevant to the protocol, but they are not considered part of the protocol. They are stored and modified separately. As such, modifications to these documents do not require protocol amendments.

# Attachment A

# Schedule of Events

Activity	Week 0	Week 1	Week 2	Week 3	Week 4	Week 5	Week 6	Week 7	Week 8	Week 9
Consent		Х								
MNSI	Х	Х								
Medical History	Х									
Height/Weight		Х					Х			
OGTT		Х								
Biweekly Health Assessment				х		Х				
VO 2 R Assessment							Х			
Plantar flexion training		Х								
Bloodwork		Х								
Actigraph**		Х	Х					Х	Х	
MRI		Х				Х				
Aerobic exercise								Х	Х	Х
Resistance exercise								Х	Х	Х
PROMIS								Х		
Calf muscle performance								Х		
9-item physical performance test								Х	Х	Х
Blood Pressure (BP)								Х	Х	Х

\*\*Actigraph to be worn for at least one week.

CONFIDENTIAL This material is the property of the NYU School of Medicine and Langone Medical Center. Do not disclose or use except as authorized in writing by the study sponsor Drug/Device Template Version: 13 JUN 2016

Page 2

# Attachment A Schedule of Events Cont....

Activity	Week 10	Week 11	Week 12	Week 13	Week 14	Week 15	Week 16	Week 17	Week 18
Consent									
MNSI									Х
Medical History									
Height/Weight								Х	
OGTT									Х
Biweekly Health Assessment									
VO 2 R Assessment								Х	
Plantar flexion training									
Bloodwork									Х
Actigraph						Х	Х		
MRI									Х
Aerobic exercise	Х	X	х	Х	х	Х	х		
Resistance exercise	Х	х	х	Х	х	Х	х		
PROMIS							х		
Calf muscle performance							х		
9-item physical performance test	X	X	X	X	X	х	X		
Blood Pressure (BP)	X	Х	Х	Х	Х	Х	х

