# 3.2 Study Endpoints

# 3.2.1 Primary Study Endpoints

Body mass index (BMI), glycosylated hemoglobin (HbA1c), and C-reactive protein will be assessed before and after the 10-week intervention, along with the following measures of neuropathic symptoms: 1) MNSI symptom questionnaire with yes/no responses to 15 items indicating the frequency and severity of neuropathic symptoms and Patient-Reported Outcomes Measurement Information System (PROMIS) Physical Function and Fatigue subscales, which are computer adaptive tools, will be used to assess symptoms related to physical disability and fatigue [52]; 2) MNSI physical exam score, to indicate abnormalities in the appearance of the feet, vibration sense, reflexes, and monofilament sensation; 3) Vibration Perception Threshold (VPT) will be assessed on the plantar aspect of the great toe [53] and Calf Muscle performance will be quantified as peak ankle plantarflexion torque at 60 degrees/sec [54]; 5) Plasma levels hydrogen peroxide as marker of ROS; 6) Lower leg muscle performance will also be assessed using the 9-item Physical Performance Test [54]; and 7) the Utah Early Neuropathy Scale, which is a physical exam specific to early sensory predominant polyneuropathy. Physical activity will be quantified using a wearable activity monitor (actigraph) [55]. Subjects will be required to wear the actigraph for at least a week.

The following outcomes will be assessed through multinuclear-MRI: 1) PCr resynthesis rate in the gastrocnemius (G) and the soleus (S) muscle groups, following a 90-s plantar flexion exercise during which resistance is applied at approximately 40% of the individual's maximum voluntary contraction (MVC); 2) Time-to-peak (TTP) of the BOLD signal in the G and S muscle groups; 3) Peak  $\Delta T2^*$  at 100% isometric MVC in the G and S muscle groups; 4) IMAT in the G and S muscle groups using IDEAL MRI; 5) Fractional anisotropy (FA) in the tibial nerve using DTI; 6) Apparent diffusion coefficient (ADC) in the tibial nerve using DTI.

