# 6.4 Study Schedule

### 6.4.1 Baseline Visit

### 6.4.1.1 Step 1: Consent

The PI, Co-Investigator, Research Coordinator, or Research Data Associate will consent individuals at the Center for Biomedical Imaging. They will go over the consent form with the subject and answer any questions that may arise. When the subject has shown that he/she understands the process and has signed the form, he/she will be given a copy of the form and considered "enrolled" in the study.

All subjects will have the option to consent remotely (through send safe) instead of consenting in person. If the subject prefers to sign the consent form electronically, the research coordinator will be able to send the informed consent via email (send safe) to the subject. The research coordinator will go over the consent form with the subject and will give ample time to the subject to ask questions regarding the study,

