### 6.4.1.3 Step 3: MRI Session

The MRIs will be performed on the day of consenting and blood tests, also at the CBI on the FDAapproved 3T whole body scanner.

All MRIs are reviewed by the licensed clinical radiologist on duty immediately as they are done. A report is issued and faxed to the PI the same day with the radiologist's interpretation of the scan as well as recommendations based on any incidental findings. In the case of an incidental finding, either the PI or another investigator on the study will speak to the subject in person at their next visit or via phone regarding the new information. Types of incidental findings would be a bone infarct, meniscal tear, or meniscal destruction found on the MRI. A copy of the original image report will also be provided to the patient in person and they will be encouraged to follow up on the discovery with their treating physician. We will ask subjects to abstain for 2 full days prior to their MRI scan from taking oral diabetes medications such as metformin. Subjects will be asked to fast the night prior to visit. Subjects will be asked to not take their insulin on the morning of their visit. All diabetes medications will be brought to the visit so that they may be taken at the conclusion of the evaluation for which they need to be fasting for.

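### Training for the in-scanner plantar-flexion task is scheduled only in the week of the first MRI, which leaves the PCr and BOLD outcomes open to a scan-1 difference of unknown size and sign

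*Combined protocol and SAP*

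**What the plan says.** - **Schedule.** Attachment A has a row "Plantar flexion training" with a single mark, in Week 1. MRI is marked in Weeks 1, 5 and 18. The Attachments page says of such material: "These documents are relevant to the protocol, but they are not considered part of the protocol".
- **Task.** Section 3.2.1 defines PCr resynthesis in the gastrocnemius and soleus "following a 90-s plantar flexion exercise during which resistance is applied at approximately 40" per cent of MVC, and peak ΔT2* "at 100% isometric MVC in the G and S muscle groups". Section 6.3 repeats the 90 seconds for the 31P task, but its Table 1 gives 2 minutes. Table 1 lists IDEAL and DTI as resting acquisitions.
- **Day of scan 1.** Section 6.4.1.3: "The MRIs will be performed on the day of consenting and blood tests, also at the CBI". Section 11.3.2: "The participant will sign the informed consent document prior to any procedures being done specifically for the study". Section 6.4.1.1 adds: "All subjects will have the option to consent remotely".
- **Contrast.** Sections 2.1 and 9.1 compare the exercise phase with the control phase, within the same person in 9.1. Section 3.1 fixes the order: 4 weeks without exercise, then 10 weeks of exercise.
- **Number of scans.** Sections 1.2 and 3.1 and Attachment A have three (baseline, pre-intervention, post-intervention). Section 9.3.1 has two, at visits 1 and 3, and section 12.3 pays for two.

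**The concern.** Both task-based outcomes depend on how hard and how skilfully the participant pushes. At scan 1 the participant is new to the task and may just have practised it with the same muscles. By scans 2 and 3 the participant has already done the task in the scanner, and no practice bout is scheduled beforehand. Everyone passes through the phases in the same order, so neither randomised order nor a concurrent group can separate familiarity from physiology. If MVC and load are not recorded at each scan, the question cannot be examined afterwards either. What is at stake is that part of a measured change in oxidative capacity or microvascular response could be an artefact of the schedule.

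**Working it through.** **1. The plan's own figure.** Inputs from section 9.4: n = 40, two-sided 5%, 80% power, SDs of change from Table 4, exercise baseline means from Table 3. Detectable change = (1.960 + 0.842) × SD / √40.

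- BOLD: 2.802 × 1.26 / 6.325 = 0.558, which is 17.2% of 3.24 (17.7% by noncentral t).
- PCr: 2.802 × 12.85 / 6.325 = 5.69, which is 13.8% of 41.16 (14.2%).
- MNSI: 2.802 × 1.78 / 6.325 = 0.788, which is 15.2% of 5.2 (15.5%).

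All three lie inside the stated 10% to 18%, so the inputs are being read as the plan used them.

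**2. Direction of a scan-1 difference.** Let S1, S2 and S3 be the readings in Weeks 1, 5 and 18. The contrast is (S3 − S2) − (S2 − S1) = S3 − 2·S2 + S1.

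- Lasting practice gain p, present in S2 and S3: the contrast changes by p − 2p = −p; S3 − S1 changes by +p; S3 − S2 does not change.
- Same-day carry-over e, present in S1 only: the contrast changes by +e; S3 − S1 changes by −e; S3 − S2 does not change.

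**3. Sensitivity range.** The documents give no value for p or e. I assume that scan 1 reads worse by d = 2% or 5% of the exercise baseline mean. The expected contrast before any shift is 1.11 − 0.18 = 0.93 for BOLD and 10.61 − 0.06 = 10.55 for PCr. With independent phases (r = 0) the SD of the contrast is √(1.26² + 1.42²) = 1.90 for BOLD and √(12.85² + 8.53²) = 15.42 for PCr. Power is from the paired t-test with n = 40.

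| Outcome | d | Contrast | Power, r = 0 | Power, r = −0.5 |
|---|---|---|---|---|
| BOLD | 0 | 0.93 | 86% | 70% |
| BOLD | 2% (0.06) | 0.87 | 80% | 63% |
| BOLD | 5% (0.16) | 0.77 | 70% | 53% |
| PCr | 0 | 10.55 | 99% | 94% |
| PCr | 2% (0.8) | 9.73 | 97% | 90% |
| PCr | 5% (2.1) | 8.49 | 92% | 80% |

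The r = −0.5 column is shown because the two phase changes share S2 with opposite signs. With equal variances and equal correlations between scans, Var = 2σ²(1 − ρ) and Cov = −σ²(1 − ρ), so r = −0.5.

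**4. False positives with no exercise effect.** For S3 − S1, using the Table 4 exercise SD, a d of 2% or 5% gives rejection rates of about 6% and 12.5% for BOLD, and 7% and 17% for PCr, against a nominal 5%. For the contrast (r = 0) a shift of the same size in either direction gives 5.5% and 8.2% for BOLD, and 6.3% and 13.1% for PCr.

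**5. In-document guide to retest drift.** The pilot control changes in Table 4 are 0.18 for BOLD (0.18 / 3.24 = 5.6%) and 0.06 for PCr (0.06 / 41.16 = about 0.15%). Both use the exercise-group baseline, because the control baseline in Table 3 could not be read in the text available to me.

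**The case against.** A reader might infer that training takes place on the day of scan 1, that scan 1 follows directly on a practice bout, and that both analyses are therefore biased. The documents do not support that much.

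- **Timing.** Attachment A gives the week only. Sections 6.4.1.3 and 11.3.2 together point to the same day, but remote consent loosens the inference. The order relative to the scan and to the two-hour glucose test, the content, and the rest are not written. If training came on an earlier day, the exertion part would fall away and the practice part would remain.
- **Sign and size.** Practice and carry-over act in opposite directions and may partly cancel. Training before scan 1 may well be intended to reduce first-scan novelty. The pilot control change for PCr is close to zero, which argues against material drift in that outcome, although it is not stated whether pilot participants had the same training.
- **Scope.** DTI and IDEAL are resting scans, and MNSI and plasma ROS do not use the task. Week 18 minus Week 5 is untouched, and section 6.4.4 speaks of comparing the final MRI with results obtained before the exercise intervention. Only a before-after change anchored at Week 1 is exposed, as section 9.3.1 has it.
- **Unseen methods.** Section 6.3 refers to sections C.1.1,2 and C.1.3, which are not in these documents. Standardisation may be described there. The documents also do not say that the MVC from scan 1 is reused.

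A second tempting reading is that section 9.4 leaves BOLD almost no room. Its printed 4.5% and 5.2% look like multiples of the control change, since 0.93 / 0.18 = 5.2. On that reading the detectable contrast is 4.5 × 0.18 = 0.81 and the margin is 0.93 − 0.81 = 0.12, or 3.7% of baseline. This implies an SD of 0.81 / 0.454 = 1.78, below the 1.90 that Table 4 gives for independent phases. At r = −0.5, power is already about 70% with no practice effect. The thin margin is therefore mainly a sample-size matter and says nothing about training.

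These objections remove any claim of demonstrated bias. They do not remove the asymmetry in the schedule.

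**Conclusion.** The point stands as an avoidable vulnerability in two outcomes, PCr resynthesis and BOLD. Familiarisation is scheduled in the week of scan 1, apparently on the same day, and is not scheduled before scans 2 and 3. In a fixed-order design, any resulting scan-1 difference passes at full size into the exercise-minus-control contrast and, with the opposite sign, into a Week 1 to Week 18 change.

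Whether such a difference exists, and which way it would run, cannot be told from the documents. The 2% to 5% range is an assumption for illustration. So is independence of the phases, under which BOLD power falls from about 86% to 80%–70% and PCr power from about 99% to 97%–92%. PCr is the less sensitive outcome. With d = 0 nothing changes. Confidence is medium. The case for acting is that the remedy is cheap and that no concurrent control can repair the problem later.

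**What to change.** In Attachment A and section 6.3:

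- Apply the same short familiarisation set, the same MVC determination and the same fixed rest before imaging at all three scans (Weeks 1, 5 and 18).
- Record MVC and the load achieved at each scan.
- If agreement between consecutive MVCs is required, use the same check, cap on attempts and rest at every scan. Open-ended practice before scan 1 alone would add to the exertion difference.

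Reconcile sections 1.2, 3.1, 9.3.1 and 12.3 with Attachment A on the number of scans and on which scan is the baseline for the before-after change. Reconcile sections 3.2.1 and 6.3 with Table 1 on task length (90 seconds or 2 minutes).

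Cost: wording in the schedule and imaging procedures, and some minutes per MRI visit with existing staff and equipment. The downside is slightly longer visits. The Attachments page says that changes to attachments need no protocol amendment; a change to section 6.3 would need one.
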